9.4.1.1 Static Physicians Global Assessment (sPGA)

The proportion of patients who achieve sPGA (0,1) and sPGA (0) will be summarized over time using descriptive statistics. A by-patient listing of sPGA scores and response rates will be provided. The listing will include patient number, treatment, timepoint, sPGA score and the sPGA response.

9.4.1.2 Psoriasis Area Severity Index (PASI)

The proportion of patients who achieve PASI 75 (at least a 75% improvement from baseline in PASI score), PASI 90 (at least a 90% improvement from baseline in PASI score) and PASI 100 (a 100% improvement from baseline in PASI score) will be summarized over time using descriptive statistics. In addition, the change from baseline and percent improvement from baseline will be summarized over time using descriptive statistics. A by-patient listing of PASI will be provided. The listing will include patient number, treatment, timepoint, PASI total score, change from baseline, percent improvement and the PASI response.

9.4.1.3 Percentage of Body Surface Area (%BSA) Assessment

The change from baseline in the %BSA will be summarized over time using descriptive statistics. A by-patient listing of %BSA will be provided. The listing will include patient number, treatment, timepoint, %BSA and change from baseline in the %BSA.

9.4.1.4 Target Engagement Assay (Total Calcitonin Gene-Related Peptide [CGRP])

Total CGRP data and its change from baseline (Day 1 predose) will be summarized by treatment and listed.

9.4.1.5 High Sensitivity-C Reactive Protein (HS-CRP)

HS-CRP data and its change from baseline (Day 1 predose) will be summarized by treatment and listed.

CCI

9.4.2 Pharmacodynamic Statistical Methodology

The PD biomarkers will be summarized by treatment and timepoint, and listed. The changes from baseline, and absolute percentage change from baseline, will also be summarized. Figures of mean values and mean changes from baseline will be presented by treatment. Individual profiles will also be plotted over time.

Analyses of PK-PD relationships will be the responsibility of Eli Lilly and Company. Refer to Section 10.3.3.1 of the protocol for additional details.

9.5 Safety and Tolerability Assessments

9.5.1 Adverse events

Where changes in severity are recorded in the Case Report Form (CRF), each separate severity of the adverse event (AE) will be reported in the listings, only the most severe will be used in the summary tables. A pre-existing condition is defined as an AE that starts before the subject has provided written informed consent and is ongoing at consent. A non-treatment emergent AE is defined as an AE which starts after informed consent but prior to dosing. A treatment-emergent AE is defined as an AE which occurs postdose or which is present prior to dosing and becomes more severe postdose. AEs by day of onset will be presented for Part B.

All AEs will be listed. Treatment-emergent AEs will be summarized by treatment, severity and relationship to the study drug. The frequency (the number of AEs, the number of subjects experiencing an AE and the percentage of subjects experiencing an AE) of treatment-emergent AEs will be summarized by treatment, Medical Dictionary for Regulatory Activities (MedDRA) version 20.0 system organ class and preferred term. The summary and frequency AE tables will be presented for all causalities and those considered related to the study drug. Any serious AEs will be tabulated.

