### 2.3. Part C (Single-Dose Study in Patients with Psoriasis)

#### Study Schedule for Protocol I9H-MC-FFAA (Part C)

	Screening	Baseline		Postdose												Extended FU	
		V1	V2	V3	V4	V5	V6	V7	V8	V9	V10	V11	V12	ED	FU a	ED	
Visit No.	V1	V2															
Study Day(s)	-33 d from Day -2	-1	1	2	4 ± 1 d	8 ± 1 d	15 ± 2 d	22 ± 2 d	29 ± 3 d	43 ± 3 d	57 ± 3 d	71 ± 3 d	85 ± 3 d	113 ± 4 d		Up to 365 ± 5 d	
Week(s)			0			1	2	3	4	6	8	10	12	16		Up to 52	
Admission to CRU		X															
Discharge from CRU				X													
Informed consent	X																
Review/confirm I/E criteria	X	X															
Complete medical history	X																
Complete physical examination	X													X			
Weight	X		X											X	X	X	
Height	X																
Symptom-directed physical examination																	
Chest x-ray	X																
Concomitant medications	X		X b	X	X	X	X	X	X	X	X	X	X	X	X	X	
Vital signs (heart rate, blood pressure, and temperature) c,d	X	X	Predose, end of infusion, and 2, 6, 12 h after SC injection e or start of infusion	24 h after SC injection e or start of infusion	X	X	X	X	X	X	X	X	X	X	X	X	
Review preexisting conditions/AEs	X		X b	X	X	X	X	X	X	X	X	X	X	X	X	X	
ECGs d,f	X																
LY3316531 administration (IV or SC)			X														

	Screening	Baseline		Postdose												Extended FU		
		Visit No.	V1	V2		V3	V4	V5	V6	V7	V8	V9	V10	V11	V12	ED	FU a	ED
Study Day(s)	-33 d from Day -2	-1	1	2	4 ± 1 d	8 ± 1 d	15 ± 2 d	22 ± 2 d	29 ± 2 d	43 ± 3 d	57 ± 3 d	71 ± 3 d	85 ± 3 d	113 ± 4 d		Up to 365 ± 5 d		
Week(s)			0			1	2	3	4	6	8	10	12	16		Up to 52		
QuantiFERON®-TB Gold test or TST	X																	
Read TST (if applicable)	X g																	
HIV/HBV/HCV	X																	
FSH h	X																	
Pregnancy test h	X	X								X		X		X	X	X	X	
Serum chemistry and hematology	X	X			X	X	X	X	X	X	X	X	X	X	X	X	X	
Urinalysis	X	X								X				X	X		X	
Urine drug screen and ethanol test	X	X																
Pharmacogenetics (exploratory storage samples for DNA)		X																
Immunogenicity d,i					See immunogenicity sampling schedule (Appendix 6)													
LY3316531 concentration (PK) d,i					See PK sampling schedule (Appendix 6)													
C-SSRS/Self-Harm Supplement and FU	X	X			X j	X	X	X	X	X	X	X	X	X	X	X	X	

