Target engagement assay (total CGRP)			X k	24 h after SC injection e or start of infusion		X	X			X		X		X	X	X	X	
Patient's Global Assessment and PSS 			X k			X	X			X		X		X	X	X	X	
PASI, sPGA, and BSA	X		X k		X	X	X			X		X		X	X	X	X	
HS-CRP	X		X k		X	X				X		X		X				
CCI Concentration			X k		X	X				X		X		X				

	Screening	Baseline		Postdose												Extended FU	
		V1	V2	V3	V4	V5	V6	V7	V8	V9	V10	V11	V12	ED	FU a	ED	
Visit No.	V1	V2															
Study Day(s)	-33 d from Day -2	-1	1	2	4 ± 1 d	8 ± 1 d	15 ± 2 d	22 ± 2 d	29 ± 3 d	43 ± 3 d	57 ± 3 d	71 ± 3 d	85 ± 3 d	113 ± 4 d	Up to 365 ± 5 d		
Week(s)			0		1	2	3	4	6	8	10	12	16		Up to 52		
Exploratory storage samples (serum, plasma, RNA)			X k			X		X		X			X				
Skin biopsy		X m				X n											

Abbreviations: AE = adverse event; BSA = body surface area; CGRP = calcitonin gene-related peptide; CRU = clinical research unit; C-SSRS = Columbia-Suicide Severity Rating Scale; d = study day; DNA = deoxyribonucleic acid; ECG = electrocardiogram; ED = early discontinuation; FSH = follicle-stimulating hormone; FU = follow-up; HBV = hepatitis B virus; HCV = hepatitis C virus; HIV = human immunodeficiency virus; HS-CRP = high sensitivity-C reactive protein; I/E = inclusion/exclusion; IL = interleukin; IV = intravenous; No. = number; PASI = Psoriasis Area and Severity Index; PK = pharmacokinetic; PSS = psoriasis symptom scale; RNA = ribonucleic acid; SC = subcutaneous; sPGA = static Physician Global Assessment; TB = tuberculosis; TST = tuberculin skin test; V = visit.

- a Monthly follow-up visits will occur during this time period for patients who respond to treatment with LY3316531 after the initial 16-week follow-up period (see Section 5.1.3 for more details).
- b At the discretion of the CRU, the baseline measurement for this assessment can be collected at any time after the patient's admission to the CRU up until LY3316531 or placebo administration on Day 1.
- c Additional vital sign measurements may be obtained when clinically indicated. Vital signs should be taken following an approximate 5-minute rest in supine position. Temperature measurement is required only at screening and baseline.
- d ECG, vital sign, and PK sampling should occur at approximately the same time. ECG recording and vital sign measurement should occur prior to the blood draw.

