### **5.1.3. Part C (Single-Dose Design in Patients with Psoriasis)**

One planned single-dose cohort will be enrolled to receive IV administration of LY3316531 with the option of 2 subsequent cohorts where the dose levels and route of administration (SC or IV) would be determined after reviewing the data from the first IV cohort.

The first cohort is planned to receive 300 mg of LY3316531 pending the analysis of available safety data from Part A. The safety scenarios for AEs, SAEs, and adverse laboratory abnormalities described in Section 7.4.2 that would prevent dose escalation in Parts A and B are the same that would prevent initiation of Part C. The actual starting dose and expected exposure will not exceed the dose/exposure that is concurrently being evaluated in Part A. Any available preliminary PK data from Cohorts 1, 2, and 3 (through Day 29) in Part A will be considered in the decision to initiate Part C as well.

Similarly, the dose for the optional cohorts will be determined based on cumulative data from previous cohorts, but will not exceed 2000 mg of LY3316531. Section 7.4.1 provides detailed information on how dose levels for the 2 optional cohorts will be determined and when the cohorts will begin enrollment procedures.

All patients who respond to LY3316531 treatment by exhibiting at least 50% reduction from baseline Psoriasis Area and Severity Index (PASI) score at Week 12 (Visit 11; Day 85) can enter an extended follow-up period for up to 52 weeks post-treatment administration (see Section 2.3). Other subjects who do not meet the above criterion for PASI reduction should be considered for discontinuation from the study at Week 16 (Visit 12; Day 113). Exceptions could be considered after a discussion between the sponsor and investigator.

A patient's participation is considered as complete if he/she received the study drug and completes all activities up to and including at least Day 85. Patients may be replaced if PK or PD data are not collected up to and including Day 85.

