investigational product (IP)	A pharmaceutical form of an active ingredient or placebo being tested or used as a reference in a clinical study, including products already on the market when used or assembled (formulated or packaged) in a way different from the authorized form, or marketed products used for an unauthorized indication, or marketed products used to gain further information about the authorized form.
investigator	A person responsible for the conduct of the clinical study at a study site. If a study is conducted by a team of individuals at a study site, the investigator is the responsible leader of the team and may be called the principal investigator.
IV	intravenous

legal representative	An individual or judicial or other body authorized under applicable law to consent, on behalf of a prospective patient/subject, to the patient's/subject's participation in the clinical study.
mAb	monoclonal antibody
MTD	maximum tolerated dose
open-label	A study in which there are no restrictions on knowledge of treatment allocation, therefore the investigator and the study participant are aware of the drug therapy received during the study.
PASI	Psoriasis Area and Severity Index
PD	pharmacodynamic(s)
PK	pharmacokinetic(s)
PSS	Psoriasis Symptom Scale
PUVA	psoralen plus ultraviolet A light therapy
QTc	QT interval
randomize	The process of assigning subjects/patients to an experimental group on a random basis.
RNA	ribonucleic acid
SAD	single-ascending dose;
SAE	serious adverse event
SC	subcutaneous
screen	The act of determining if an individual meets minimum requirements to become part of a pool of potential candidates for participation in a clinical study.
SUSAR	suspected unexpected serious adverse reaction
TB	tuberculosis
TBL	total bilirubin level
TE	treatment emergent
TEAE	treatment-emergent adverse event: Any untoward medical occurrence that emerges during a defined treatment period, having been absent pretreatment, or worsens relative to the pretreatment state, and does not necessarily have to have a causal relationship with this treatment
Th	T helper
TNF	tumor necrosis factor

**TST** tuberculin skin test

**ULN** upper limit of normal

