5.3 Part C (Single-Dose Design in Patients with Psoriasis)

One planned single-dose cohort will be enrolled to receive IV administration of LY3316531 with the option of 2 subsequent cohorts where the dose levels and route of administration (SC or IV) would be determined after reviewing the data from the first IV cohort.

The first cohort is planned to receive 300 mg of LY3316531 pending the analysis of available safety data from Part A. The actual starting dose and expected exposure will not exceed the dose/exposure that is concurrently being evaluated in Part A. Any available preliminary PK data from Cohorts 1, 2, and 3 (through Day 29) in Part A will be considered in the decision to initiate Part C as well. Similarly, the dose for the optional cohorts will be determined based on cumulative data from previous cohorts, but will not exceed 2000 mg of LY3316531.

All patients who respond to LY3316531 treatment by exhibiting at least 50% reduction from baseline Psoriasis Area and Severity Index (PASI) score at Week 12 (Visit 11; Day 85) can enter an extended follow-up period for up to 52 weeks post-treatment administration. Other subjects who do not meet the above criterion for PASI reduction should be considered for discontinuation from the study at Week 16 (Visit 12; Day 113). Exceptions could be considered after a discussion between the sponsor and investigator.

A patient's participation is considered as complete if he/she received the study drug and completes all activities up to and including at least Day 85. Patients may be replaced if PK or PD data are not collected up to and including Day 85.

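### Part C TEAE and SAE percentages have no common observation window and follow-up depends on response, so they partly reflect responder share and enrolment timing

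*SAP*

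**What the plan says.** SAP 9.5.1 (Adverse events) sets the rule: "A treatment-emergent AE is defined as an AE which occurs postdose or which is present prior to dosing and becomes more severe postdose". It names no last day. The planned TEAE summaries include "the percentage of subjects experiencing an AE", by treatment and without person-time; serious AEs are tabulated. The one display organised by time is confined to the multiple-dose part: "AEs by day of onset will be presented for Part B". The protocol glossary (Appendix 1) is narrower. It defines a TEAE as "Any untoward medical occurrence that emerges during a defined treatment period, having been absent pretreatment", but neither document dates such a period for Part C.

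Follow-up in Part C depends on outcome. Under SAP 5.3 and Protocol 5.1.3, a patient whose PASI has fallen by at least half at Week 12 "can enter an extended follow-up period for up to 52 weeks post-treatment administration". For the rest, Protocol 5.1.3 says: "Other subjects who do not meet the above criterion for PASI reduction should be considered for discontinuation from the study at Week 16". Exceptions are possible after sponsor and investigator confer. Footnote a of the Part C schedule (Protocol 2.3) confirms the extra visits: "Monthly follow-up visits will occur during this time period for patients who respond to treatment with LY3316531 after the initial 16-week follow-up period". The schedule row "Review preexisting conditions/AEs" is marked in the extended follow-up columns. Under Protocol 9.2.1, the duty to look actively for AEs ends when a person completes or leaves the study.

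SAP 10 starts the analysis for the clinical study report (CSR) once everyone has reached Day 85 (Part A), Day 141 (Part B) or Day 113 (Part C), or has left early. It covers the data available at that point. No Part C data cut is stated.

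**The concern.** Incidence of AEs, TEAEs and SAEs is the primary endpoint. A crude percentage is interpretable only over a known length of observation. In Part C that length is about 16 weeks for non-responders. For responders it is whatever has accrued by the CSR, up to 52 weeks. A cohort with more responders, or one enrolled earlier, is watched for longer and can show a higher percentage with no difference in the drug's effect on AEs. If optional Part C cohorts run at other doses, a more active dose could look less safe for this reason alone. Even with a single cohort, the reported percentage has no stated time base.

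**Working it through.** **The plan's own figures.** No AE rate, responder share or expected shift is stated. The only size figures are enrolment, and they reproduce: 46 + 16 + 24 = 86 planned and 52 + 20 + 30 = 102 maximum. A Part C cohort has 7 or 8 patients (Protocol Table FFAA.5.1), so one patient is 14.3 or 12.5 points.

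**Responder follow-up at the CSR (T), from the sequencing rules, with instant enrolment.**
- One optional Part C cohort opens after 4 weeks of PASI data from at least 7 patients (Protocol 7.4.1): 4 + 16 = 20 weeks for Cohort 1.
- Two optional Part C cohorts in sequence: 4 + 4 + 16 = 24 weeks.
- No optional cohort, but the trigger waits for Part B (Protocol 7.4.2, SAP 10). Take a Part C patient dosed as Part A Cohort 4 opens, and 14 days (Day 1 to Day 15) for each of Cohorts 4, 6 and 7: 3 × 14 + 140 = 182 days = 26 weeks.
- As above, plus the optional Part B cohort, which opens 15 days after the second dose: 182 + 28 + 14 = 224 days = 32 weeks.
- Reading the 15-day rule as 15 full days gives 185 days (26.4 weeks) and 228 days (32.6 weeks).

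The last two paths run from the earliest possible Part C dose. A later Part C start shortens them; slower accrual in Parts A or B lengthens them.

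**Model (assumed).** The first-AE hazard h is constant at 0.02 to 0.05 per week, so F(t) = 1 − exp(−ht). Non-responders are followed for 16 weeks. With k responders of 8, crude incidence = [(8 − k)F(16) + kF(T)]/8. Going from k = 2 to k = 6 shifts it by 0.5 × [F(T) − F(16)]. F(16) is 27.4% at h = 0.02 and 55.1% at h = 0.05. Shifts below use unrounded values.

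| T (weeks) | F(T), h = 0.02 / 0.05 | k = 2 vs 6, h = 0.02 | k = 2 vs 6, h = 0.05 | Patients of 8 |
|---|---|---|---|---|
| 20 | 33.0 / 63.2% | 28.8 vs 31.6 (+2.8) | 57.1 vs 61.2 (+4.1) | 0.2–0.3 |
| 24 | 38.1 / 69.9% | 30.1 vs 35.4 (+5.4) | 58.8 vs 66.2 (+7.4) | 0.4–0.6 |
| 26 | 40.5 / 72.7% | 30.7 vs 37.3 (+6.6) | 59.5 vs 68.3 (+8.8) | 0.5–0.7 |
| 32 | 47.3 / 79.8% | 32.4 vs 42.3 (+9.9) | 61.3 vs 73.6 (+12.4) | 0.8–1.0 |
| 52 | 64.7 / 92.6% | 36.7 vs 55.3 (+18.6) | 64.4 vs 83.2 (+18.8) | 1.5 |

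The shift peaks inside the hazard range for the last two rows. At T = 32 it is 0.5 × (0.500 − 0.250) = 12.5 points (h = 0.043). At T = 52 it is 0.5 × (0.592 − 0.182) = 20.5 points, 1.6 patients (h = 0.033).

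**Enrolment timing alone.** Suppose two optional Part C cohorts run, Part C sets the trigger, and every cohort has 6 responders. Cohort 1 then exceeds Cohort 3 by 0.75 × [F(24) − F(16)] = 8.1 to 11.1 points.

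**Lower hazard after Week 16.** If the late hazard is half the early one, the 2-versus-6 shift is 3.5 to 5.0 points at T = 26 and 5.4 to 7.4 at T = 32. At a quarter, it is 1.8 to 2.6 and 2.8 to 4.1.

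**SAEs.** Assume a 16-week risk p of 2% to 5%, so h = −ln(1 − p)/16 = 0.0013 to 0.0032. The same shift is 0.2 to 2.4 points for T = 20 to 32 (at most 0.19 of a patient) and 2.2 to 5.2 points at T = 52 (at most 0.41).

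**Noise.** With n = 8, k = 4 and T = 20 to 32, the binomial standard error is about 16 to 17 points.

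**The case against.** The case for leaving the plan alone has several parts.

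- Day 113 could be meant as the cut. SAP 10, however, gives it as a milestone that starts the analysis, alongside two other parts' milestones, and then uses available data. If a cut is intended, one sentence settles it; the effect would then leave the CSR and appear only in an addendum.
- The table shells are a separate document and may impose a window. That cannot be excluded, but the SAP text states none.
- All AEs are listed, so a Day 113 count can be made by hand. True, but the primary endpoint is reported as summary percentages.
- The late hazard may be lower. Visits become monthly, and with the anticipated half-life of 2 to 3 weeks (Protocol 5.4) five half-lives are 10 to 15 weeks. This stands and shrinks the shift.
- Only one Part C cohort is firmly planned, Part C has no placebo arm, SAP 9.5.15 plans no inference, and the shift at 20 to 32 weeks is below one standard error. All true. The shift is nevertheless systematic and linked to response, and a stated window removes it.

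A reader might infer more than the documents support. The window is not unlimited: collection ends at study exit, so what is missing is a common window. Healthy-subject follow-up is not response-dependent, so Parts A and B are not affected. Dose decisions do not rest on these percentages. The Week 52 figure is not the expected CSR result: it needs every responder to stay, and the protocol has patients leave extended follow-up when they need further treatment.

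**Conclusion.** The point holds for Part C. As written, the plan gives primary-endpoint percentages over unequal windows whose length depends on response and calendar time. Its size cannot be fixed from the documents. Under a constant hazard of 0.02 to 0.05 per week and a 2-versus-6 responder contrast in a cohort of 8, it runs from about 3 points at 20 weeks to about 12 at 32 weeks, with 20.5 as the Week 52 ceiling. It is smaller if the hazard falls after Week 16. SAE shifts stay below half a patient under the stated risks. Neither a large shift nor a negligible one is established. The consequence is descriptive: it affects how the Part C safety profile reads, and affects a between-cohort contrast only if optional cohorts run. The change is worth making because it is cheap and the endpoint is primary.

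**What to change.** In SAP 9.5.1, present Part C TEAE and SAE incidence for all patients over Day 1 to Day 113, and use that table for any comparison between cohorts. Tabulate events with onset after Day 113 separately, with person-time. Keep an all-follow-up summary, because Protocol 6.3.4 predicts relevant exposure (stated for contraception) for 5 months after the last dose: about 152 days or 21.7 weeks, beyond Day 113. State the Part C AE data cut in SAP 10.

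With the common window, the response-dependent shift is zero by construction; unequal follow-up from early drop-out remains. The cost is a few lines of SAP text and one or two extra Part C tables, with no change to data collection.

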9.5.2 Concomitant medication

Concomitant medication will be coded using the WHO drug dictionary (Version March 2017). Concomitant medication will be listed.

9.5.3 Clinical laboratory parameters

All clinical chemistry and hematology data will be summarized by parameter and treatment, and listed. Urinalysis data will be listed. Additionally clinical chemistry, hematology and urinalysis data outside the reference ranges will be listed.

Values for any clinical chemistry, hematology and urinalysis values outside the reference ranges will be flagged on the individual subject data listings.

9.5.4 Vital signs

Vital signs data will be summarized by treatment together with changes from baseline, where baseline is defined as Day 1 predose. Figures of mean vital signs and mean changes from baseline profiles by treatment will be presented by treatment.

Furthermore, values for individual subjects will be listed.

9.5.5 Electrocardiogram (ECG)

The ECG data will be obtained directly from the 12-lead ECG traces. These data include the PR, QT, QTcB intervals, QRS duration and heart rate, where QTcB is the QT interval corrected using Bazett's formula. In addition, QTcF (the QT interval corrected using Fridericia's formula) will be calculated as follows:

$$QTcF = \frac{QT}{\sqrt[3]{(60/HR)}}$$

The ECG data will be summarized by treatment together with changes from baseline, where baseline is defined as Day 1 predose. Figures of mean ECG data and mean changes from baseline will be presented by treatment. The frequency of subjects with a maximum increase from baseline in QTcB and QTcF interval will be summarized for each treatment according to the following categories: >30 ms and >60 ms. In addition, the frequency of subjects with QTcB and QTcF postdose values, according to the following categories: >450 ms, >480 ms and >500 ms, will be summarized by treatment.

A plasma LY3316531 concentration-QT analysis will be performed to assess the changes from baseline (Day 1 predose) QTcF interval relative to plasma LY3316531 concentrations across all active treatments. The change from baseline adjustment will be based on individual subject's Day 1 predose value. The analysis will be performed by plotting change from baseline QTcF against LY3316531 concentrations, including all post Day 1 dosing timepoints. The plot will be produced separately for parts A, B, and C of the study. Each plot will include a simple linear regression.

